Use of Convalescent Plasma Collected From Donors Recovered From COVID-19 Virus
Disease for Transfusion, as an Empirical and Preemptive Treatment during Viral
Pandemic Outbreak

Principal Investigator: [name]

Protocol version: 12/7/2020

Protocol Summary

Study Title: Use of Convalescent Plasma Transfusion, Collected From Donors Recovered From COVID-19 Virus Disease, as an Empirical and Preemptive Treatment during Pandemic Outbreak

Phase II

Expected Numbers of Patients:

Group 3: High risk patients n=159
Group 4: Health Care Providers n=152

Study Objectives:

- 1. To transfuse COVID-19 infected patients with convalescent plasma and to observe whether this will result in a significant improvement in clinical outcome in comparison to historical experience. Patients eligible include the following study groups:
- **Group 3:** As preemptive therapy for High Risk Patients who present with mild or non-severe COVID-19 infection.
- **Group 4:** As preemptive therapy for health care providers who have developed asymptomatic, mild or non-severe COVID-19 infection.
- **a. Primary objective** is whether infusion of convalescent plasma will reduce the probability of progressing to severe or critical disease significantly lower than the reported case rate (for Group 3 and 4, respectively).
- **b. Secondary objectives** are to determine if infusion of convalescent plasma will impact the patient's clinical course including days in hospital, days requiring ICU care, days on mechanical respirator/BIPAP, days on non-mechanical oxygen support, days with pneumonia, fever, and viral clearance.

Overview of Study Design

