Group sequential design is employed for each hypothesis that analysis will be performed after enrolling and observing outcomes of one-third of maximum sample size. Our design includes two interim analyses and a final analysis for each hypothesis. The Pocock method is used to determine sample size and each study is sized to maintain the power of 80% and overall type I error 5%. To calculate the sample size, the large-sample Z test for a proportion is utilized for each analysis. The maximum number of enrollment for the four groups are: Group 1: 81, Group 2: 423, Group 3: 228 and Group 4: 219. Due to the likelihood that we may terminate a study for efficacy after an interim analysis, the expected numbers of enrollment for the four groups are 56, 296, 152 and 152, respectively.

[figure not shown]
Study Population: Eligible patients will be 18 years or older and must have a positive test result for COVID-19 infection to and meet the inclusion criteria described in Section 4.1

Duration of Study: 24 months

Participant Duration: 30 days or in the case of hospitalization, upon discharge; whichever

is longer.

Schema: Convalescent Plasma Treatment for COVID-19 Infection

Definitions:

COVID-19 severity categories:

- Mild No pneumonia but with typical symptoms such as fever, dry cough, fatigue, nausea, emesis or diarrhea.
- Non-severe Radiographic changes compatible with viral PNA, but no signs of respiratory compromise or hypoxemia.
- •Severe Respiratory compromise with one of the following: Tachypnea with RR ≥30, O₂ Sat ≤93% at rest, PaO₂/FiO₂ index ≤ 300 mmHg
- Critical One of the following: requiring mechanical ventilation, requiring pressor support, multiorgan failure.

Patient Risk Category:

High risk:

- •Immunocompromised (e.g. neutropenia, h/o hematopoietic stem cell transplant (<3 months post-autologous transplant, <6 months post-allogeneic transplant), on systemic immunosuppression, h/o solid organ transplant, Cancer patient receiving active chemotherapy, insulin dependent diabetes mellitus, poorly controlled HIV, moderate or severe asthma history, serious heart condition, ESRD on hemodialysis, morbid obesity, moderately severe or greater COPD.
- •Age ≥ 65 years

Contents

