In a larger report from Chinese Center for Disease Control and Prevention of 72,314 cases 14% presented with severe disease that was defined as dyspnea, respiratory frequency \geq 30, blood oxygen saturation \leq 93%, partial pressure of arterial oxygen to fraction of inspired oxygen ratio < 300, and/or lung infiltrates >50% within 24-48 hours.** Critical disease developed in 5% that resulted in respiratory failure, septic shock and/or multi-organ failure. In this report the case fatality rate (CFR) was 8.0% in patients age 70-79, 14.8% in patients over age 80, and 49% in critical cases. CFR was elevated among those with preexisting comorbid conditions: 10.5% for cardiovascular disease, 7.3% for diabetes, 6.3% for chronic respiratory disease, 6.0% for hypertension and 5.6% for cancer. A total of 1,716 infected were health care workers. Overall, 14.8% of health care workers developed severe or critical disease, and 5 deaths were observed.**

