1.3 High Risk Clinical Characteristics of COVID-19 Disease

High risk groups for developing severe COVID-19 infection have been defined by the Center of Diseases and Control Prevention (CDC) and include: xxvi

- Persons 65 years and older
- Chronic Lung disease
- Moderate to Severe Asthma
- Serious Heart Conditions
- Immunocompromised patients (including undergoing cancer treatment, bone marrow or organ transplantation, immune deficiency diseases, poorly controlled HIV or AIDS, prolonged use of corticosteroids and other immune weakening medications (e.g. cyclosporine, tacrolimus, etc.)
- Severe obesity (BMI of 40 or higher)
- Diabetes
- Chronic Kidney disease and undergoing dialysis
- Liver Disease

On 3/26/2020, the FDA release selection criteria for COVID-19 disease to be eligible for donor convalescent plasma who met their definition for severe disease or immediately life-threatening status.

Severe disease is defined as:

- Dyspnea
- Respiratory frequency ≥ 30/min
- Blood oxygen saturation < 93%
- Partial pressure oxygen to fraction of inspired oxygen ratio <300, and/or
- Lung infiltrates > 50% within 24 to 48 hours

Life-threatening disease is defined as:

- Respiratory failure
- Septic shock, and/or
- Multiple organ dysfunction or failure

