3.1.1 Primary and Secondary Endpoints and Efficacy Assessments

The primary endpoint of the study will be:

- 1) progression to severe disease for those with high-risk disease that present with mild/non-severe disease, and
- 2) progression to severe disease for health care workers who present with asymptomatic, mild or non-severe disease.

Secondary endpoints will include:

- 1) Acute care facility/hospital length of stay
- 2) Number of days requiring oxygen support
- 3) Number of days in an intensive care unit
- 4) Number of days on mechanical ventilation (invasive, noninvasive and ECMO)
- 5) Incidence of viral disease associated cardiomyopathy
- 6) Incidence of multi-organ dysfunction/failure
- 7) Safety of transfusion—Incidence of severe adverse events

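### Group 4: the protocol's Severe category is narrower than the definition described for the report behind the 14.8% null, and the endpoint does not say which definition governs

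*Combined protocol and SAP*

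**What the plan says.** **The trial's category.** The Definitions in the Protocol Summary give Severe as "Respiratory compromise with one of the following: Tachypnea with RR" of 30 or more, oxygen saturation of 93% or less at rest, or PaO2/FiO2 of 300 mmHg or less. Dyspnea and extent of infiltrates are not listed. Non-severe is "Radiographic changes compatible with viral PNA, but no signs of respiratory compromise or hypoxemia", with no limit on radiographic extent.

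**The source's category.** Section 1.2 reports that, among 72,314 Chinese cases, 14% "presented with severe disease that was defined as dyspnea, respiratory frequency" of 30 or more, saturation of 93% or less, PaO2/FiO2 below 300, "and/or lung infiltrates >50% within 24-48 hours". The same paragraph then states: "Overall, 14.8% of health care workers developed severe or critical disease".

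**A third list.** Section 1.3 prints the FDA plasma-eligibility definition of severe disease, which again has dyspnea and "Lung infiltrates > 50% within 24 to 48 hours".

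**Objective, endpoint and test.** The stated objective is to "reduce the probability of progressing to severe or critical disease significantly lower than the reported case rate". Section 3.1.1 gives the Group 4 endpoint as "progression to severe disease for health care workers who present with asymptomatic, mild or non-severe disease". Section 6.1 takes 14.8% as the reference rate and plans for 7.5%, with three stages of 73 patients. Section 6.3 claims efficacy at any look where the upper score limit, with critical value 2.289, is below the null. None of 3.1.1, 6.1 and 6.3 refers to a definition of severe.

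**The concern.** A single-arm test against a published rate is fair only if the trial and the source count the same event. Here, a health care worker who became breathless, or whose infiltrates passed 50%, without meeting the rate, saturation or PaO2/FiO2 threshold, may be an event in the 14.8% and a non-event in the trial. The missing events all push one way: the observed rate falls below the null even if plasma does nothing.

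The Group 4 conclusion rests entirely on the upper limit against 14.8%, so no concurrent arm would reveal the discrepancy. Section 6.3 allows reassessment of case rates from CDC updates and plans a later comparison with published experience. Section 6.2 plans historical or matched comparisons for secondary endpoints. None of these aligns the definitions or shows how far a claim depends on them.

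**Working it through.** **Inputs.** Null p0 = 0.148, planned p1 = 0.075, stages 73/146/219 (Section 6.1); c = 2.289, score upper limit below p0 (Section 6.3). The share f of source severe-or-critical cases that met only dyspnea or infiltrates over 50% is not in the documents; the values used are assumptions.

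**1. Reproduce the plan's size.** The fixed-sample Z test with null variance, two-sided 5% and 80% power, gives (1.960 + 0.842)² × 0.148 × 0.852 / 0.073² = 185.7. Multiplying by the three-look Pocock inflation factor 1.165 gives 216.4, or 72.1 per stage, rounded up to 73. The maximum is 3 × 73 = 219, as printed.

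**2. Efficacy limits.** With p = x/n, the score upper limit is

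U = [p + c²/(2n) + c√(p(1−p)/n + c²/(4n²))] / (1 + c²/n).

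For 20/219: (0.0913 + 0.0120 + 0.0461) / 1.0239 = 0.1459, below 0.148. For 21/219, U = 0.1513, which is not. The same calculation at the other looks gives limits of 3/73, 11/146 and 20/219.

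**3. False-efficacy chance.** For an inert product, if all else is comparable, the rate counted in the trial is 0.148 × (1 − f). Exact three-stage binomial enumeration, stopping at the first look that meets its limit:

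| f (assumed) | Rate counted in trial | Chance of efficacy claim |
|---|---|---|
| 0 | 14.8% | 1.4% |
| 5% | 14.1% | 2.7% |
| 10% | 13.3% | 5.0% |
| 20% | 11.8% | 14.9% |

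The efficacy side of the 2.289 rule corresponds to about 2.5%. The exact chance passes that level at about f = 4.3%, and passes 5% at about f = 9.9%.

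**4. Largest f that a claim survives.** A claim still holds against a null of 0.148 × (1 − f) while f is below 1 − U/0.148. At the three limits:

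| Events | U | 1 − U/0.148 |
|---|---|---|
| 3/73 | 0.1317 | 11.0% |
| 11/146 | 0.1413 | 4.5% |
| 20/219 | 0.1459 | 1.4% |

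**5. What that report would show at the planned effect.** The chance of a claim at a true 7.5% is 86.4%. The chance of a claim that also survives f = 10% is 59.5%, so 1 − 0.595/0.864 = 31% of claims would not survive. If f is real and the trial rate scales with it, to 7.5% × 0.9 = 6.75%, the two chances are 93.9% and 72.7%, and about 23% would not survive.

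**The case against.** The strongest reply is that the mismatch rests on links the documents do not settle.

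- The endpoint does not cite the Summary definition. Under the Section 1.3 list there would be no such gap. That list is background on FDA eligibility, and the Summary text is the only one headed as severity categories, so the Summary reading is the likelier one. It is still a reading.
- Section 1.2 attaches the wider definition to the 14% figure, not expressly to the health care workers' 14.8%. It gives no other severe definition for that report, but the link is inferred.
- The source list ends in and/or, which leaves open whether dyspnea alone qualified.
- Nothing bounds f. It could be very small.

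All four stand. They limit the point to a possible bias of unknown size.

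Three stronger readings are tempting and are not supported. A reader might infer from the table that the Group 4 error rate is inflated to 5% or 15%; those values follow only from assumed f. A reader might infer the opposite, that all is well if f is below about 4%. That requires 14.8% to fit the enrolled patients in every other respect, yet Sections 3.1.2.2 and 4.1.2 admit asymptomatic and administrative staff and limit entry to people not already severe, while the source figure comes from reported cases. A reader might also extend the point to Group 3; the documents show no such bias there.

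**Conclusion.** The documents establish that the Group 4 endpoint does not name its definition of severe, and that the protocol's own category omits two items described for the source of its null. If the Summary definition governs and the wider definition underlies the 14.8%, the discrepancy can only lower the trial's count on those two items. The one difference found in the other direction, PaO2/FiO2 at or below 300 against below 300, is trivial.

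The size is unknown. The calculated false-efficacy chances are conditional on assumed f and on otherwise comparable patients, and case mix is a separate source of non-comparability that they do not measure. What can be said without knowing f is how fragile a claim is: one made exactly at the final limit fails if as little as 1.4% of source events fall outside the trial's definition, while one made exactly at the first limit tolerates 11.0%. Severity is minor to moderate.

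**What to change.** 1. Reconcile the severe definitions in the Protocol Summary, Section 1.2 and Section 1.3. State in 3.1.1, 6.1 and 6.3 which definition of severe or critical governs the endpoint, and how it compares with the one behind the 14.8%.
2. Leave the primary test and stopping rule as they are. With any Group 4 efficacy claim, report once the largest f it survives, 1 − U/0.148, and word the conclusion accordingly. A grid of alternative nulls at every look is not needed, since it would inform no decision, and a claim should not have to survive any set range of f.
3. Optionally, list new dyspnea descriptively where it is already recorded. Section 5.1.1 documents it before infusion; Section 5.1.3.2 asks for a symptom diary but does not name dyspnea as an item. Scoring of infiltrates over 50% should not be required: Section 5.1.3.4 calls for follow-up films only where a baseline film exists, and the plan provides no reading of percentage involvement.

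The cost is a few cross-references and one reported figure, with no added patients, visits or films. Because the test is unchanged, exact power stays at 86% at the planned 7.5%. The downside is a more qualified conclusion: at the planned effect, about 31% of claims would not survive f = 10% if the trial rate stays at 7.5%, or about 23% if it scales with f.

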9.0 References

1.0 Study Rationale

Convalescent plasma has been utilized for over one-hundred years for the empirical treatment of viral pandemics and has been reported to reduce duration of symptoms and mortality risk. Preliminary evidence indicates that convalescent plasma may possibly be of benefit for some patients with COVID-19, leading to clinical improvement.

1.1 Background and Rationale

1.1.1 Introduction

Since the early twentieth century convalescent plasma has been used during pandemics including the 1918 H1N1 Influenza virus pandemic (Spanish Flu), vi poliomyelitis vii, measles, viii, ix mumps, x 2009-2010 H1N1 Influenza virus pandemic, xi SARS-1 in 2003 in and Middle East respiratory syndrome (MERS) in 2012. xiv, xv The most recent example is the West Africa Ebola epidemic, which was associated with a high mortality risk with no known drug or vaccine therapy. A small nonrandomized trial demonstrated significantly improved survival for those who received convalescent whole blood, and two patients urgently transferred to the United States and treated with a combination of convalescent plasma survived. xvi,xvii,xviii

While every viral disease and epidemic are different, immunological responses are similar and these historical precedents provide both reassuring and useful data in developing a treatment protocol using convalescent plasma for COVID-19 disease.

1.1.2 Rationale for using COVID-19 convalescent plasma Experience with the use of convalescent plasma against coronavirus diseases

In the past two decades there have been two epidemics with coronavirus that resulted in high mortality, SARS-1 in 2003 and Middle East respiratory syndrome (MERS) in 2012. The latter infections became an endemic in the Middle East and triggered a secondary outbreak in South Korea. Due to the high mortality and lack of an effective therapy, convalescent plasma was utilized. The largest report involved 80 patients with severe SARS disease in Hong Kong.⁹ For patient who received convalescent plasma transfusion prior to day 14 of the infection have an improved prognosis and an earlier hospital discharge prior to day 22 (58.3% vs 15.6%, P<.001). The mortality rates in the two groups were 6.3% and 21.9%, respectively. This observation is consistent with the prior historical observations that earlier administration in the course of the infection is more likely to be effective. Convalescent plasma given to three patients in Taiwan with severe SARS disease resulted in reduction the serum virus titer and each survived.¹⁰

China has offered convalescent plasma therapy for 245 COVID-19 patients, and 91 cases have shown improvement in clinical indicators and symptoms, per press report. Treatment of five critically ill patients in China with COVID-19 and acute respiratory distress syndrome (ARDS) with convalescent plasma was followed by resolution of ARDS in 4 patients within 9 days following transfusion. Of the 5 patients 3 had been discharged and 2 were in stable condition at 37 days post-transfusion. In a third report, 10 patients with severe COVID-19 infection received one dose of convalescent plasma derived from recently recovered donors. The primary endpoint was safety of plasma infusion and secondary endpoint was efficacy. Clinical symptoms improved along with improved oxygenation within 3 days of transfusion. The viral load was undetectable after transfusion in the seven of seven patients who had detection pretreatment at a median of 3 days (2-6 days). Cytokine surrogate marker, Creactive protein, fell from a median before transfusion of 55.98 mg/L (nl range 0 – 6) to 18.13 following the treatment. No serious adverse reactions or safety events were recorded.

[figure not shown]

Figure 1. Schematic of the use of convalescent sera for COVID-19. An individual who is sick with COVID-19 and recovers has blood drawn and screened for virus-neutralizing antibodies. Following identification of those with high titers of neutralizing antibody, serum containing these virus-neutralizing antibodies can be administered in a prophylactic manner to prevent infection in high-risk cases, such as vulnerable individuals with underlying medical conditions, health care providers, and individuals with exposure to confirmed cases of COVID-19. Additionally, convalescent serum could potentially be used in individuals with clinical disease to reduce symptoms and mortality. The efficacy of these approaches is not known, but historical experience suggests that convalescent sera may be more effective in preventing disease than in the treatment of established disease.²

1.2 Clinical Characteristics of COVID-19 Disease

In the largest published review from Wuhan China, 1099 patients were followed with confirmed COVID-19 infection. A primary composite end-point event occurred in 67 patients (6.1%), including 5% who were admitted to the ICU, 2.3% who underwent invasive mechanical ventilation, and 1.4% who died. The majority of patients (58%) received intravenous antibiotic therapy and oxygen was administered in 41.3% of patients. CT radiograph was performed on 975 patients and it showed ground-glass opacities in 56.4%, local patchy shadowing in 41.9% and bilateral patchy shadowing in 51.8% and interstitial abnormalities in 14.7%. Chest radiographs were performed in 274 patients and abnormalities were documented in 59.1% (20.1%, 28.1%, 36.5% and 4.4%; respectively). In severe cases, radiographic abnormalities were seen on CT study in 94.6% of patients. For hospitalized patients, fever was present in 88.1% of non-severe and 91.9% of severe patients.

A total of 173 patients were classified as having severe disease per the guidelines of the American Thoracic Society guidelines. For those 926 that presented with non-severe disease, 35.7% required oxygen, 2.4% required ICU admission and none required mechanical ventilation. For those with severe disease, 71.1% required oxygen therapy, 19.1% were admitted to the ICU and 38.7% required mechanical ventilation. The median length of hospital stay for the non-severe was 11 days (10-13) and for the severe 13 days (11.5-17). Death occurred in 0.1% of the patients with non-severe disease and 8.1% of patients with severe disease. For patients presenting with severe disease 71.1% required oxygen therapy, 15.6% developed acute respiratory distress syndrome, admission to the ICU was 19.1%, 38.7 percent required mechanical ventilation (14.5% invasive and 32.4% noninvasive) and median hospital duration was 13 days.

Correlate laboratory studies included C-reactive protein that was elevated above 10 mg/L in 81.5% of those with severe disease and in 56.4% with non-severe disease. Procalcitonin

greater than 0.5 ng/mL was seen in only 3.7% of those with non-severe disease and 13.7% with severe disease presentation.

In a larger report from Chinese Center for Disease Control and Prevention of 72,314 cases 14% presented with severe disease that was defined as dyspnea, respiratory frequency \geq 30, blood oxygen saturation \leq 93%, partial pressure of arterial oxygen to fraction of inspired oxygen ratio < 300, and/or lung infiltrates >50% within 24-48 hours.** Critical disease developed in 5% that resulted in respiratory failure, septic shock and/or multi-organ failure. In this report the case fatality rate (CFR) was 8.0% in patients age 70-79, 14.8% in patients over age 80, and 49% in critical cases. CFR was elevated among those with preexisting comorbid conditions: 10.5% for cardiovascular disease, 7.3% for diabetes, 6.3% for chronic respiratory disease, 6.0% for hypertension and 5.6% for cancer. A total of 1,716 infected were health care workers. Overall, 14.8% of health care workers developed severe or critical disease, and 5 deaths were observed.**

1.3 High Risk Clinical Characteristics of COVID-19 Disease

High risk groups for developing severe COVID-19 infection have been defined by the Center of Diseases and Control Prevention (CDC) and include: xxvi

- Persons 65 years and older
- Chronic Lung disease
- Moderate to Severe Asthma
- Serious Heart Conditions
- Immunocompromised patients (including undergoing cancer treatment, bone marrow or organ transplantation, immune deficiency diseases, poorly controlled HIV or AIDS, prolonged use of corticosteroids and other immune weakening medications (e.g. cyclosporine, tacrolimus, etc.)
- Severe obesity (BMI of 40 or higher)
- Diabetes
- Chronic Kidney disease and undergoing dialysis
- Liver Disease

On 3/26/2020, the FDA release selection criteria for COVID-19 disease to be eligible for donor convalescent plasma who met their definition for severe disease or immediately life-threatening status.

Severe disease is defined as:

- Dyspnea
- Respiratory frequency ≥ 30/min
- Blood oxygen saturation < 93%
- Partial pressure oxygen to fraction of inspired oxygen ratio <300, and/or
- Lung infiltrates > 50% within 24 to 48 hours

Life-threatening disease is defined as:

- Respiratory failure
- Septic shock, and/or
- Multiple organ dysfunction or failure

